13.2. Sample Size Determination

A sample size of 30 subjects per group provides adequate precision for the estimated treatment difference for the incidence of adverse withdrawal events during an opioid taper. Precision of the estimated difference is quantified by the width of the 95% confidence interval for the treatment difference. When the difference in proportions is 0.2, the 95% confidence interval is 0.2 ± 0.24 when n=20/group and is 0.20 ± 0.17 when n=40/group (Figure 2).

[figure not shown]

Figure 2: Width of 95% Confidence Interval as a Function of Sample Size

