Dosing of study drug will continue for 5 days after the last opioid dose. Study drug will then be tapered over an additional 4 days (Section 9.2.3).

Subjects will be given a diary to take home and will use it to complete daily questionnaires regarding withdrawal and other symptoms, average and worst daily pain, record opioid and study drug administration and concomitant treatment use (including use of medication for pain or opioid withdrawal symptoms).

Subjects will take their blood pressure and heart rate at home using a vital sign monitor. At home readings will be collected during phone calls conducted by study staff after each opioid dose reduction and twice daily (morning and evening) during the 4-day study drug taper through the End of Study (EOS) Visit. Subjects will record readings in their diary.

Subjects will return to the clinic on Day 3, Day 8, and then on a weekly basis following randomization during study drug administration for assessments. With the exception of Day 1 (Visit 1), clinic visits can occur \pm 1 day from the study-specified timepoint. Subjects will return to the clinic approximately 7 days after their last dose of study drug. At 30 days following the last dose of study drug, subjects will receive a telephone call for a safety follow-up and assessment of the subject's current opioid usage, after which their participation in the study will be complete.

Subjects who prematurely discontinue the study will be instructed to taper study drug as described in Section 9.2.3 and to complete the at-home assessments for the study drug taper period (Table 4 or Table 5). Once discontinued, subjects may not re-enter the study.

Number of Subjects:

60 subjects (30 LUCEMYRA, 30 placebo)

A sample size of 30 subjects per group provides adequate precision for the estimated treatment difference for the incidence of adverse withdrawal events during opioid taper. Precision of the estimated difference is quantified by the width of the 95% confidence interval for the treatment difference.

Diagnosis and Main Criteria for Eligibility:

Inclusion Criteria

- 1. Subject can provide written informed consent.
- 2. Subject is willing and able to comply with scheduled visits, treatment plan, laboratory tests, and other study procedures.
- 3. Chronic non-cancer pain diagnosis such as low back pain, chronic neck pain, osteoarthritis, and prolonged post-surgical pain with daily pain for a minimum of 6 months.

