- Percentage of subjects identified as suicide risk with C-SSRS.

Effectiveness:

The following effectiveness endpoints will assess withdrawal symptoms and pain:

- Percentage of subjects who successfully complete each scheduled dose reduction and the opioid taper to complete opioid discontinuation, with or without a pause.
- Change in COWS from Baseline to peak value and to each scheduled evaluation.
- Change in SOWS-H from Baseline to peak value and to each scheduled evaluation.
- Change in SOWS-Gossop from Baseline to peak value and to each scheduled evaluation.
- MCGI-R by each scheduled evaluation.
- MCGI-S by each scheduled evaluation.
- Time to study drug discontinuation.
- Change in daily opioid dose, expressed as MED, and as a percentage of the baseline MED.
- Number of non-opioid concomitant medications for withdrawal symptoms used by study day.
- Change in average and worst daily pain from Baseline to peak value as measured by the NRS.
- Change in EQ-5D-5L from Baseline to each scheduled evaluation.
- Change in SF-36 from Baseline to each scheduled evaluation.
- Change in ISI from Baseline to each scheduled evaluation.
- Change in HADS from Baseline to each scheduled evaluation.

Statistical Methods:

The treatment group difference in proportions will be summarized descriptively with a 95% confidence interval. The 95% confidence interval will be calculated based on the normal approximation for the binomial distribution, using the Wald continuity correction. In addition, the treatment group difference will be tested with Cochran-Mantel-Haenszel (CMH) test stratified by total opioid dose (<90 MED, \geq 90 MED.

The treatment group difference for mean change will be summarized descriptively with 95% confidence intervals. The 95% confidence intervals for the treatment group differences will be calculated within the framework of analysis of covariance (ANCOVA). The ANCOVA will have treatment and total opioid dose (<90 MED, \geq 90 MED) as fixed factors and baseline as covariate. In addition, the treatment group difference will be tested within the ANCOVA framework.

[figure not shown]
Safety data will be summarized with descriptive statistics. Adverse events (AEs) will be categorized by system organ class and preferred term with the Medical Dictionary for Regulatory Activities.

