7.3. Number of Subjects

A total of 60 subjects will be randomized in a 1:1 ratio to LUCEMYRA (30 subjects) and placebo (30 subjects).

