13.4. Statistical Analyses

13.4.1. Effectiveness Analyses

13.4.1.1. Successful Completion of Opioid Taper

The treatment group difference in the proportion of subjects who successfully complete the opioid taper will be summarized descriptively with a 95% confidence interval. The 95% confidence interval will be calculated based on the normal approximation for the binomial distribution, using the Wald continuity correction [(1/n1 + 1/n2)/2]. In addition, the treatment group difference will be tested with Cochran-Mantel-Haenszel (CMH) test stratified by total opioid dose (<90 MED, \geq 90 MED) in ITT population.

The percentage of subjects who meet each of the components of successful completion of opioid taper will be summarized.

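### The half-widths of ±0.24 (n=20) and ±0.17 (n=40) supporting 30 per group omit the continuity correction that the plan prescribes for a difference in proportions

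*Combined protocol and SAP*

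**What the plan says.** Section 7.3 sets the size: "A total of 60 subjects will be randomized in a 1:1 ratio to LUCEMYRA (30 subjects) and placebo (30 subjects"). Section 13.2 gives the reason, in a sentence about events while the opioid is being tapered: "A sample size of 30 subjects per group provides adequate precision for the estimated treatment difference for the incidence of adverse withdrawal events during an" (cut just before the sentence ends). Both 13.2 and the Synopsis (Number of Subjects) state how precision is measured: "Precision of the estimated difference is quantified by the width of the 95% confidence interval for the treatment difference". The only numbers offered are in 13.2: "When the difference in proportions is 0.2, the 95% confidence interval is 0.2 ± 0.24 when n=20/group and is 0.20 ± 0.17 when n=40/group". The readable text of 13.2 names neither the interval formula nor the two event rates, and gives no half-width at the planned 30 per group. It refers to Figure 2, which is not shown in the copy reviewed.

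On the interval itself, the Synopsis (Statistical Methods) says, without naming an endpoint: "The treatment group difference in proportions will be summarized descriptively with a 95% confidence interval". It continues: "The 95% confidence interval will be calculated based on the normal approximation for the binomial distribution, using the Wald continuity correction". Section 13.4.1.1, on successful completion of the opioid taper, gives the size of the correction: "using the Wald continuity correction [(1/n1 + 1/n2)/2"]. No other interval for a difference in proportions is named in the document.

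**The concern.** The two half-widths stand in the ratio 0.24/0.17 = 1.41, which is √2. An interval whose width depends on n only through 1/√n behaves this way when n doubles from 20 to 40. A continuity correction of 1/n shrinks faster than 1/√n, so it would disturb that ratio. This suggests that the planning figures come from a narrower interval than the one the plan says it will report.

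Interval width is the only stated basis for 30 per group. The Synopsis rationale says the pilot is meant to inform the design of a pivotal study, so a reader may carry these figures forward. Someone planning from 13.2 would expect tighter intervals than the prescribed method will give.

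**Working it through.** **Inputs**
- Difference 0.20, with half-widths 0.24 at n=20 and 0.17 at n=40 per group (13.2).
- 95% two-sided confidence, z = 1.96 (13.2).
- Planned n = 30 per group, 1:1 (7.3).
- Continuity correction (1/n1 + 1/n2)/2 (13.4.1.1). With equal arms this is 1/n: 0.050, 0.033 and 0.025 at n = 20, 30 and 40.
- Event rates: not stated in the readable text.

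**Reproducing the stated figures.** For the uncorrected Wald interval, half-width = 1.96 × √{[p1(1−p1) + p2(1−p2)]/n}. With 10% versus 30% (an assumption), the bracket is 0.09 + 0.21 = 0.30.
- n=20: 1.96 × √(0.30/20) = 0.240
- n=40: 1.96 × √(0.30/40) = 0.170

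Both stated figures are recovered. The mirror pair, 70% versus 90%, gives the same values.

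**Test that needs no event rates.** With the prescribed correction, half-width = A/√n + 1/n. The constant A absorbs the event rates, the choice of pooled or unpooled variance, and the confidence level. Allowing for rounding:
- 0.24 at n=20 means 0.235 to 0.245. Then A = (0.235 − 0.05)√20 to (0.245 − 0.05)√20 = 0.827 to 0.872. At n=40 this gives 0.156 to 0.163, which never prints as 0.17.
- 0.17 at n=40 means 0.165 to 0.175. Then A = (0.165 − 0.025)√40 to (0.175 − 0.025)√40 = 0.885 to 0.949. At n=20 this gives 0.248 to 0.262, which prints as 0.25 or 0.26, never 0.24.

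The two ranges of A do not overlap, so the pair of figures cannot include the 1/n correction. Without a correction, 0.235 to 0.245 at n=20 implies 0.166 to 0.173 at n=40, which agrees with 0.17.

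**Scan over rates.** The lower rate p was moved in steps of 0.0001, with the other rate at p + 0.20 and results rounded to two decimals. With +1/n, no pair fits both figures under either unpooled or pooled variance. The forms that do fit are listed below (mirror rates also fit). The third column is the half-width each form implies at n=30. The last column is the prescribed interval (unpooled Wald plus 1/n) at the same rates.

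| Form behind the stated figures | Lower rate | Implied at n=30 | Prescribed at n=30 |
|---|---|---|---|
| Unpooled, no correction | 9.0–11.1% | 0.192–0.200 | 0.225–0.233 |
| Pooled, no correction | 7.4–9.4% | 0.192–0.200 | 0.218–0.227 |
| Unpooled, correction 1/(2n) | 5.5–6.2% | 0.193–0.196 | 0.209–0.213 |
| Pooled, correction 1/(2n) | 4.1–4.8% | 0.193–0.196 | 0.202–0.206 |

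**Size at 10% versus 30%**

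| n per group | Uncorrected | Prescribed (+1/n) |
|---|---|---|
| 20 | 0.240 | 0.290 |
| 30 | 0.196 | 0.229 |
| 40 | 0.170 | 0.195 |

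At these rates the prescribed interval at 40 per group (0.195) is about as wide as the uncorrected one at the planned 30 (0.196).

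**The case against.** The strongest reply is that 13.2 concerns adverse withdrawal events, which are safety data. Section 13.4.2 makes all safety summaries descriptive with no testing, and 13.4.2.1.1 lists only counts and percentages. The correction formula appears under effectiveness, for taper completion. The Synopsis paragraph goes on to a Cochran-Mantel-Haenszel test, so it may simply condense 13.4.1.1 and not reach adverse events at all. On that reading, 13.2 and 13.4.1.1 concern different endpoints and do not conflict.

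Part of this stands: the link to adverse withdrawal events does rest on the general Synopsis sentence. But that sentence presents the interval as a descriptive summary, which is compatible with 13.4.2. Section 13.2 itself relies on a 95% interval for this difference, and the plan names no other. If the sponsor intends a different interval for withdrawal events, 13.2 still needs to say which.

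Three further points are fair. The figures are not miscalculated, because they are right for an uncorrected Wald interval at suitable rates; the fault is a mismatch with the prescribed method. A simplified planning formula is also acceptable if it is declared, but the readable text does not declare one, and at these sample sizes the correction is not negligible. Finally, Figure 2 is unseen and may give the method, the rates or the n=30 value. It could supply what the text lacks, but it could not make the two printed figures consistent with a 1/n correction.

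**Conclusion.** The concern holds. The two half-widths in 13.2 cannot both come from the continuity-corrected interval, whatever the event rates; this conclusion needs only the stated figures, the stated correction and ordinary rounding. That the corrected interval applies to adverse withdrawal events rests on the general wording of the Synopsis.

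The size does depend on inferred rates. If the figures are uncorrected Wald half-widths, the understatement at n=30 is about 0.03. Under the other forms that fit, it runs from about 0.03 down to about 0.01. The severity is minor: the plan claims only adequate precision, sets no maximum width and makes no power claim, so no criterion is missed and 30 per group need not change.

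**What to change.** In 13.2, name the interval and the assumed event rates, and restate the half-widths for the prescribed interval, including the planned 30 per group. If the sponsor confirms the inferred rates, the text could read: *Assuming event rates of 10% and 30%, the half-width of the continuity-corrected Wald 95% confidence interval is 0.29, 0.23 and 0.19 at 20, 30 and 40 subjects per group.* If other rates were used, the same sentence applies with the corresponding values. Redraw Figure 2 if it was drawn without the correction.

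The cost is one or two sentences and possibly one figure. No subjects are added and no analysis changes. The stated precision becomes less favourable by up to about 0.03 at n=30.

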13.3. Analysis Populations

Analysis populations are defined in Table 12.

Analysis Population	Description	
Safety	All subjects who take at least 1 dose of study drug. Subjects will be analyzed according to the treatment they actually received.	
Intent-to-Treat	nt-to-Treat All subjects in the Safety Population who have at least 1 effectiveness assessment after Baseline. Subjects will be analyzed according to the treatment they are actually randomized to.	

Table 12:Analysis Populations

13.4. Statistical Analyses

13.4.1. Effectiveness Analyses

13.4.1.1. Successful Completion of Opioid Taper

The treatment group difference in the proportion of subjects who successfully complete the opioid taper will be summarized descriptively with a 95% confidence interval. The 95% confidence interval will be calculated based on the normal approximation for the binomial distribution, using the Wald continuity correction [(1/n1 + 1/n2)/2]. In addition, the treatment group difference will be tested with Cochran-Mantel-Haenszel (CMH) test stratified by total opioid dose (<90 MED, \geq 90 MED) in ITT population.

The percentage of subjects who meet each of the components of successful completion of opioid taper will be summarized.

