9. TREATMENT OF SUBJECTS

9.1. Randomization and Blinding

9.1.1. Randomization

Eligible subjects will be randomized in a 1:1 ratio to LUCEMYRA or placebo. The randomization will be stratified by total opioid dose, in MED, captured at Screening (<90 MED, \geq 90 MED). The subject's baseline opioid use and changes to doses for planned taper reductions should be submitted to and approved by the Medical Monitor prior to Day -1.

Subject randomization will be performed using a computer-generated randomization schedule, providing site staff with a randomization code linked to the study drug kit number to be used.

Hard copies of the study drug randomization schedule will be stored securely. Only medically necessary unblinding(s) will be allowed.

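### Taper-completion confidence interval is unstratified and continuity-corrected while its companion test is stratified: the interval is conservative, moderately too wide, and can include zero when the test is significant

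*Combined protocol and SAP*

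**What the plan says.** Section 13.4.1.1 states that the treatment difference in the proportion completing the taper "will be summarized descriptively with a 95% confidence interval". The interval is "calculated based on the normal approximation for the binomial distribution, using the Wald continuity correction", and the correction is written out as (1/n1 + 1/n2)/2. No stratification is attached to the difference or to its interval. The same section says the difference will be "tested with Cochran-Mantel-Haenszel (CMH) test stratified by total opioid dose" in the ITT population.

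The Statistical Methods part of the synopsis (Section 3.1) repeats the arrangement for proportions in general: "The treatment group difference in proportions will be summarized descriptively with a 95% confidence interval" by the same method, and "the treatment group difference will be tested with Cochran-Mantel-Haenszel (CMH) test stratified by total opioid dose". Section 9.1.1 shows where the strata come from: "The randomization will be stratified by total opioid dose, in MED, captured at Screening", cut at 90 MED. Section 7.3 fixes 30 subjects per arm.

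The continuous endpoints are handled differently. The ANCOVA models in the synopsis and in Sections 13.4.1.2, 13.4.1.5 and 13.4.1.6 include dose stratum as a fixed factor, so their treatment differences are stratum-adjusted. The interval for proportions is the exception, and no reason is given.

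**The concern.** There are two separate problems.

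- **The correction.** It adds a fixed 1/30 to each side of the interval whatever the data show. It is meant to offset the under-coverage of the plain Wald interval, but at 30 per arm it overshoots at most plausible rates.
- **The strata.** The interval ignores the factor used in the randomization and in the test. If completion depends on baseline dose, the pooled variance contains between-stratum variation that the CMH test removes.

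Both push the same way, so the interval tends to be wider than its 95% label warrants. The secondary objectives in Section 6.2 are framed as estimating treatment differences, and the synopsis says the pilot is to inform the design of a pivotal trial. Unneeded width therefore has some cost. The more visible consequence is that one table could show a CMH p-value below 0.05 beside a 95% interval that includes zero, with nothing in the plan to say which governs.

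**Working it through.** **Inputs.** From the documents: 30 per arm (7.3); correction (1/n1 + 1/n2)/2 (13.4.1.1); strata below 90 and 90 MED or more (9.1.1); CMH test with no continuity correction mentioned (13.4.1.1). Assumed, because the documents do not give them: completion rates, stratum sizes, and the difference in completion between strata (stratum gap).

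**1. The plan's only printed precision figures.** Section 13.2 gives half-widths of 0.24 at 20 per group and 0.17 at 40 per group for a difference of 0.2. They concern adverse withdrawal events, not taper completion, but they show the scale. The plain Wald half-width is 1.96 × √[(p1q1 + p2q2)/n]. With rates 0.1 and 0.3 (not stated; they fit), p1q1 + p2q2 = 0.09 + 0.21 = 0.30:
- n = 20: 1.96 × √(0.30/20) = 0.240
- n = 40: 1.96 × √(0.30/40) = 0.170

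Both figures are reproduced without the correction.

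**2. Size of the correction at 30 per arm.** (1/30 + 1/30)/2 = 0.0333. At the same rates the half-width rises from 1.96 × √(0.30/30) = 0.196 to 0.229, and 0.0333/0.196 = 17%.

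**3. Coverage and width, strata ignored** (exact binomial enumeration, 30 per arm).
- For differences of 0.2, from 0.1/0.3 to 0.7/0.9, the planned interval covers 96.5-97.2%.
- Over all rates from 0.05 to 0.95, mean coverage is 96.8% (planned), 93.8% with a minimum of 80.5% (plain Wald), 95.0% (Newcombe) and 95.1% (Miettinen-Nurminen).
- For the same 0.2 differences, the planned interval is wider by 14-17% than plain Wald, 14-16% than Miettinen-Nurminen and 15-20% than Newcombe.
- Near 0.95 in both arms it is narrower than Newcombe or Miettinen-Nurminen.

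**4. Effect of ignoring the strata** (simulation, 15 + 15 per arm, true difference 0.2). The comparator is a stratum-weighted Wald-type interval with variance divisor n.

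| Overall rates | Stratum gap | Planned coverage | Planned width / stratified width |
|---|---|---|---|
| 0.6 / 0.4 | 0 | 96.5% | 1.16 |
| 0.6 / 0.4 | 0.4 | 97.8% | 1.27 |
| 0.8 / 0.6 | 0 | 96.8% | 1.17 |
| 0.8 / 0.6 | 0.4 | 98.3% | 1.31 |

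This comparator itself covers only about 93-94%, so the ratios flatter it. With divisor n-1 they become 1.12, 1.23, 1.13 and 1.27.

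**5. A concrete disagreement.** Completers on drug: 12/15 and 8/15 by stratum. On placebo: 8/15 and 4/15.
- CMH, first stratum: expected 15 × 20/30 = 10, observed 12, variance 15 × 15 × 20 × 10/(30² × 29) = 1.724.
- CMH, second stratum: expected 15 × 12/30 = 6, observed 8, variance 15 × 15 × 12 × 18/(30² × 29) = 1.862.
- Chi-square = (2 + 2)²/(1.724 + 1.862) = 4.46, p = 0.035.
- Planned interval: difference 20/30 - 12/30 = 0.267; standard error √[(0.2222 + 0.2400)/30] = 0.1241; half-width 1.96 × 0.1241 + 0.0333 = 0.277; interval -0.010 to 0.543.
- Without the correction: 0.023 to 0.510.

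**6. How often.** Over assumed scenarios with a true effect, the CMH test was significant while the planned interval included zero in about 7-16% of simulated trials. The low end goes with little or no stratum effect and the high end with a large one. Under no effect it was about 2%. The reverse did not occur.

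**7. Why a stratified score interval agrees with the test.** Take Mantel-Haenszel weights w = n1n2/N and the Miettinen-Nurminen null variance pq(1/n1 + 1/n2) × N/(N-1), with p the pooled stratum rate and q = 1 - p. Each w²V reduces to n1n2pq/(N-1), which is the CMH variance term. In the example w = 7.5, Σw·d = 7.5 × (4/15 + 4/15) = 4 and Σw²V = 3.586, giving 4.46 again. The interval excludes zero whenever the uncorrected CMH test is significant.

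**The case against.** The case for leaving the plan alone has real weight. The interval is labelled descriptive. Taper completion is one of 14 effectiveness endpoints under a secondary objective; the primary objective is safety, with no testing (13.4.2). No decision rule uses this interval or test, and Section 13.5 has no formal futility analysis. A continuity-corrected Wald interval is recognised and fully specified here, and it protects against the under-coverage of plain Wald. The error is on the safe side. All of this stands and holds the severity down.

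Two further defences stand only in part. Section 13.1 leaves details to a statistical analysis plan whose text is not available here, so a supportive stratified interval cannot be ruled out; but 13.4.1.1 already names the method, and a deferral does not undo that. If the CMH test were run with a continuity correction, the example would give (4 - 0.5)²/3.586 = 3.42, below 3.84, and the disagreement would vanish; but the plan mentions no such correction for the test.

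Stronger readings are tempting and not supported:
- A reader might infer that the trial's size rests on this interval. The width argument in Section 13.2 is about adverse withdrawal events, so this point gives no ground for redrawing Figure 2.
- A reader might take an excess of 21-26% as a property of the plan. At 30 per arm against plain Wald that requires p1q1 + p2q2 between 0.197 and 0.128, that is, rates near 0 or 1. Otherwise it requires a particular stratified comparator with assumed stratum effects.
- A reader might treat any stratified interval as a full cure. In simulation stratified Newcombe still disagreed with the CMH test in up to about 5-6% of trials, depending on rates and construction.

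**Conclusion.** The point holds at low severity. The plan pairs an unstratified, continuity-corrected interval with a stratified test. At 30 per arm and assumed mid-range completion rates, the nominal 95% interval covers about 96.5-98%, the upper end arising when completion differs strongly by dose stratum. It is roughly 14-20% wider than standard near-nominal intervals. Precision scales with 1/√n, so that is the width such an interval would give with about 30/1.20² = 21 to 30/1.14² = 23 subjects per arm. The excess could be greater against a stratified interval if dose is strongly prognostic, and it disappears near 95% completion in both arms.

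Disagreement with the CMH test is possible and not rare: about 7-16% of trials under the assumed effects, always with the test significant and the interval including zero. With a modest stratum effect most of this comes from the correction; lack of stratification matters more as the stratum gap grows.

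These sizes rest on assumed rates, strata of 15 + 15 or 20 + 10 per arm, and an uncorrected CMH test. The existence of the mismatch does not depend on the assumed rates. It biases no estimate toward a false claim of benefit and threatens no stated decision.

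**What to change.** In Section 13.4.1.1 and the Statistical Methods part of the synopsis:

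- Report the difference in completion as a Mantel-Haenszel-weighted risk difference stratified by MED (below 90, 90 or more), with a stratified Miettinen-Nurminen (score) 95% interval.
- Use the same method for the proportion completing each scheduled dose reduction, an endpoint in Section 7.2.2.
- State that the CMH test is run without a continuity correction, so that test and interval agree.
- State in advance what is done if a dose stratum is sparse or empty in either arm, for example the unstratified Miettinen-Nurminen interval with the corresponding unstratified test.

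Do not simply delete the continuity correction: the plain Wald interval would then under-cover (mean 93.8%, minimum 80.5% at 30 per arm).

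The cost is a few lines of text, slightly more programming and the sparse-stratum rule. Sample size, data collection and conduct do not change. The edit should be made before the analysis plan is finalized.
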